13.3.2 ECI Reporting Guidelines

ECIs are selected non-serious and serious adverse experiences that must be reported to Merck **within 24 hours** regardless of attribution to study treatment. The AEs listed in this document and any event that meets the ECI criteria (as noted) in Table 1 or in the respective protocol (event term and Grade) must be reported regardless of physician-determined causality with study medication and whether or not considered immune-related by the physician (unless otherwise specified). Physicians/study coordinators/designated site personnel are required to record these experiences as ECIs on the Adverse Experience electronic Case Report Forms (eCRFs) (or on paper) and to provide supplemental information (such as medical history, concomitant medications, investigations, etc.) about the event.

- Please refer to the Data Entry Guidelines (DEGs) for your protocol.
- Please refer to protocol for details on reporting timelines and reporting of Overdose and Drug Induced Liver Injury (DILI).

13.3.3 ECI Categories and Terms

This section describes the ECI categories and outlines subject management guidelines when an ECI is reported.

13.3.4 Pneumonitis

The following AE terms, if considered \geq Grade 2, are considered ECIs and should be reported to the Drug Manufacturer within 24 hours of the event:

- Pneumonitis
- Interstitial lung disease
- Acute interstitial pneumonitis

If symptoms indicate possible new or worsening cardiac abnormalities additional testing and/or a cardiology consultation should be considered.

All attempts should be made to rule out other causes such as metastatic disease, bacterial or viral infection. **It is important that patients with a suspected diagnosis of pneumonitis be managed as per the guidance below until treatment-related pneumonitis is excluded. Treatment of both a potential infectious etiology and pneumonitis in parallel may be warranted. Management of the treatment of suspected pneumonitis with steroid treatment should not be delayed for a therapeutic trial of antibiotics.** If an alternative diagnosis is established, the patient does not require management as below; however the AE should be reported regardless of etiology.

Course of Action

Grade 2 events:

- Report as ECI
- Hold pembrolizumab.
- Consider pulmonary consultation with bronchoscopy and biopsy/BAL.
- Consider ID consult
- Conduct an in person evaluation approximately twice per week
- Consider frequent Chest X-ray as part of monitoring
- Treat with systemic corticosteroids at a dose of 1 to 2 mg/kg/day prednisone or equivalent. When symptoms improve to Grade 1 or less, steroid taper should be started and continued over no less than 4 weeks.
- Permanently discontinue for inability to reduce corticosteroid dose to 10 mg or less of prednisone or equivalent per day within 12 weeks.
- Second episode of pneumonitis – discontinue pembrolizumab if upon re-challenge the patient develops a second episode of Grade 2 or higher pneumonitis.

Grade 3 and 4 events:

- Report as ECI
- Discontinue pembrolizumab.
- Hospitalize patient
- Bronchoscopy with biopsy and/or BAL is recommended.
- Immediately treat with intravenous steroids (methylprednisolone 125 mg IV). When symptoms improve to Grade 1 or less, a high dose oral steroid (prednisone 1 to 2

- mg/kg once per day or dexamethasone 4 mg every 4 hours) taper should be started and continued over no less than 4 weeks.
- If IV steroids followed by high dose oral steroids does not reduce initial symptoms within 48 to 72 hours, treat with additional anti-inflammatory measures. Discontinue additional anti-inflammatory measures upon symptom relief and initiate a prolonged steroid taper over 45 to 60 days. If symptoms worsen during steroid reduction, initiate a retapering of steroids starting at a higher dose of 80 or 100 mg followed by a more prolonged taper and administer additional anti-inflammatory measures, as needed
 - Add prophylactic antibiotics for opportunistic infections.

13.3.5 Colitis

The following AE terms, if considered \geq Grade 2 or resulting in dose modification **or use of systemic steroids to treat the AE**, are considered ECIs and should be reported to the Drug Manufacturer within 24 hours of the event:

- Colitis
- Colitis microscopic
- Enterocolitis
- Enterocolitis hemorrhagic
- Gastrointestinal perforation
- Intestinal obstruction
- Necrotizing colitis
- Diarrhea

All attempts should be made to rule out other causes such as metastatic disease, bacterial or parasitic infection, viral gastroenteritis, or the first manifestation of an inflammatory bowel disease by examination for stool leukocytes, stool cultures, a Clostridium difficile titer and endoscopy. However the AE should be reported regardless of etiology.

Course of Action

Grade 2 Diarrhea/Colitis (4-6 stools/day over baseline, dehydration requiring IV fluids < 24 hours, abdominal pain, mucus or blood in stool):

- Report as ECI
- Hold pembrolizumab.
- Symptomatic Treatment
- For Grade 2 diarrhea that persists >1 week, and for diarrhea with blood and/or mucus,
 - Consider GI consultation and endoscopy to confirm or rule out colitis
 - Administer oral corticosteroids (prednisone 1-2 mg/kg QD or equivalent)
- When symptoms improve to Grade 1 or less, steroid taper should be started and continued over no less than 4 weeks.

- Permanently discontinue for inability to reduce corticosteroid dose to 10 mg or less of prednisone or equivalent per day within 12 weeks.
- If symptoms worsen or persist > 3 days treat as Grade 3

Grade 3 Diarrhea/Colitis (or Grade 2 diarrhea that persist for greater than 3 days):

- Report as ECI
- Hold pembrolizumab.
- Rule out bowel perforation. Imaging with plain films or CT can be useful.
- Recommend consultation with Gastroenterologist and confirmation biopsy with endoscopy.
- Treat with intravenous steroids (methylprednisolone 125 mg) followed by high dose oral steroids (prednisone 1 to 2 mg/kg once per day or dexamethasone 4 mg every 4 hours) When symptoms improve to Grade 1 or less, steroid taper should be started and continued over no less than 4 weeks. Taper over 6 to 8 weeks in patients with diffuse and severe ulceration and/or bleeding.
- Permanently discontinue for inability to reduce corticosteroid dose to 10 mg or less of prednisone or equivalent per day within 12 weeks.
- If IV steroids followed by high dose oral steroids does not reduce initial symptoms within 48 to 72 hours, consider treatment with additional anti-inflammatory measures as described in the literature [5]. Discontinue additional anti-inflammatory measures upon symptom relief and initiate a prolonged steroid taper over 45 to 60 days. If symptoms worsen during steroid reduction, initiate a retapering of steroids starting at a higher dose of 80 or 100 mg followed by a more prolonged taper and administer additional anti-inflammatory measures as needed.

Grade 4 events:

- Report as ECI
- Permanently discontinue pembrolizumab.
- Manage as per Grade 3.

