Diarrhea / Colitis	Grade 2 or 3	Withhold	
 • Administer corticosteroids (initial dose of 1-2 mg/kg prednisone or equivalent) followed by taper 	
 • Monitor participants for signs and symptoms of enterocolitis (ie, diarrhea, abdominal pain, blood or mucus in stool with or without fever) and of bowel perforation (ie, peritoneal signs and ileus). • Participants with \geq Grade 2 diarrhea suspecting colitis should consider GI consultation and performing endoscopy to rule out colitis. • Participants with diarrhea/colitis should be advised to drink liberal quantities of clear fluids. If sufficient oral fluid intake is not feasible, fluid and electrolytes should be substituted via IV infusion.
	Grade 4	Permanently discontinue		

AST / ALT elevation or Increased bilirubin	Grade 2	Withhold	
 Administer corticosteroids (initial dose of 0.5- 1 mg/kg prednisone or equivalent) followed by taper 	
 Monitor with liver function tests (consider weekly or more frequently until liver enzyme value returned to baseline or is stable)
	Grade 3 or 4	Permanently discontinue	
 Administer corticosteroids (initial dose of 1-2 mg/kg prednisone or equivalent) followed by taper 	
Type 1 diabetes mellitus (T1DM) or Hyperglycemia	Newly onset T1DM or Grade 3 or 4 hyperglycemia associated with evidence of β -cell failure	Withhold	
 Initiate insulin replacement therapy for participants with T1DM Administer anti-hyperglycemic in participants with hyperglycemia 	
 Monitor participants for hyperglycemia or other signs and symptoms of diabetes.
Hypophysitis	Grade 2	Withhold	
 Administer corticosteroids and initiate hormonal replacements as clinically indicated. 	
 Monitor for signs and symptoms of hypophysitis (including hypopituitarism and adrenal insufficiency)
	Grade 3 or 4	Withhold or permanently discontinue ¹		
Hyperthyroidism	Grade 2	Continue	
 Treat with non-selective beta-blockers (eg, propranolol) or thionamides as appropriate 	
 Monitor for signs and symptoms of thyroid disorders.
	Grade 3 or 4	Withhold or permanently discontinue ¹		

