Each of the events above is described within this guidance paragraph, along with site requirements for reporting these events to the Drug Manufacturer. The information collected should be entered into the narrative field(s) of the Adverse Event module in the database (please note, if narrative entry into the database is not available, please use the narrative text box on the 1727/AER Form). If additional Medical History or Concomitant Medications are reported, the Medical History and Concomitant Medication modules in the database must be updated.

In addition, the guidelines include recommendations on the management of these ECIs. These guidelines are intended to be applied when the physician determines the events to be

related to pembrolizumab. Note: if after the evaluation the event is determined not to be related, the physician is instructed to follow the ECI reporting guidance but does not need to follow the treatment guidance (below). Therefore, these recommendations should be seen as guidelines and the treating physician should exercise individual clinical judgment based on the patient. For any question of dose modification or other treatment options, the specific language in the protocol should be followed. Any questions pertaining to the collection of this information or management of ECIs should be directed to your local Drug Manufacturer contact.

Dose Modification/Discontinuation

The treatment guidance provides specific direction when to hold and/or discontinue pembrolizumab for each immune related adverse event. Of note, when the guidance states to “discontinue” pembrolizumab this is the permanent discontinuation of treatment with pembrolizumab. “Hold” means to stop treating with pembrolizumab but resumption of treatment may be considered assuming the patient meets the criteria for resumption of treatment (see Section 8.1.5.2.1).

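### In Section 13.3.5 the 3-day escalation rule for Grade 2 diarrhea makes the 1-week oral-steroid trigger unreachable, and the Section 6.2.1.2 table states no duration at all

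*Combined protocol and SAP*

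**What the plan says.** Three places in the combined protocol and SAP tell the investigator when to give steroids for Grade 2 diarrhea.

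- **Section 13.3.5, Grade 2 list, steroid bullet.** The condition is "For Grade 2 diarrhea that persists >1 week, and for diarrhea with blood and/or mucus". The action is "Administer oral corticosteroids (prednisone 1-2 mg/kg QD or equivalent").
- **Section 13.3.5, last bullet of the Grade 2 list, and the Grade 3 heading.** The bullet reads "If symptoms worsen or persist > 3 days treat as Grade 3". The heading reads "Grade 3 Diarrhea/Colitis (or Grade 2 diarrhea that persist for greater than 3 days"). The action under that heading is "Treat with intravenous steroids (methylprednisolone 125 mg) followed by high dose oral steroids".
- **Section 6.2.1.2, immune-related AE table, diarrhea/colitis row.** Grade 2 and Grade 3 share one entry: pembrolizumab is withheld and the instruction is "Administer corticosteroids (initial dose of 1-2 mg/kg prednisone or equivalent) followed by taper". No duration is given.

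Section 13.3.1 says how the guidance relates to the rest of the protocol: "For any question of dose modification or other treatment options, the specific language in the protocol should be followed". It also describes the recommendations as guidelines that leave room for individual judgment, to be applied when the physician considers the event related to pembrolizumab. Section 6.2.1.2, in turn, refers the reader to Section 13.3 for the management of adverse events.

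**The concern.** Two duration limits, 3 days and 1 week, sit in one short list and lead to different steroid routes. The shorter limit leads to the more intensive route, so the longer one appears to have no role. A reader who takes the 1-week bullet as the Grade 2 rule would wait where a reader who takes the last bullet would escalate.

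What is at stake is whether a patient with uncomplicated Grade 2 diarrhea receives no steroids, oral steroids or intravenous steroids. Steroid use also feeds into the rules for resuming and stopping pembrolizumab, so the choice can reach beyond the episode itself. This is a safety instruction, and it should not depend on which line the investigator reads first.

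**Working it through.** The plan gives no figure to reproduce here. The check is a comparison of texts plus the ordering of two time limits.

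**Inputs.** Steroid bullet: more than 1 week, i.e. more than 7 days, or blood or mucus at any time (Section 13.3.5). Escalation bullet and Grade 3 heading: more than 3 days (Section 13.3.5); the bullet also covers worsening symptoms. Diarrhea/colitis row: no duration (Section 6.2.1.2).

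**Step 1: order of the limits.** Since 3 < 7, every episode that exceeds 7 days exceeded 3 days earlier, and the gap is 7 − 3 = 4 days. No episode can first meet the 1-week condition while it is still under Grade 2 management. The blood or mucus condition has no waiting period, so it can still apply first.

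**Step 2: one episode, three sources.** Take Grade 2 diarrhea without blood, mucus or worsening.

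| Time since onset | 1-week bullet | 3-day bullet and Grade 3 heading | Section 6.2.1.2 row |
|---|---|---|---|
| Days 1 to 3 | not met; hold and symptomatic treatment | not met | corticosteroids; no duration stated |
| Days 4 to 7 | not met | met; intravenous, then high-dose oral | as above |
| After day 7 | met; oral | met since day 4 | as above |

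On days 4 to 7 an investigator guided by the 1-week bullet has no steroid instruction yet, while one guided by the 3-day rule goes to intravenous treatment. After day 7 the two conditions are both met and name different first actions.

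**Step 3: can the 3-day bullet mean 3 days despite oral steroids?** It follows the steroid bullets, so read alone it could. The Grade 3 heading closes off that reading. It says "or Grade 2 diarrhea that persist for greater than 3 days", which counts days of Grade 2 diarrhea and does not mention prior steroids.

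**Step 4: does a precedence rule settle it?** Section 13.3.1 defers to the protocol, which could favor the Section 6.2.1.2 row over Section 13.3.5. Section 6.2.1.2 points back to Section 13.3. Whichever way that is read, it ranks one section against another and cannot rank two lines within Section 13.3.5.

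**Step 5: what changes downstream.** Under the general instructions in Section 6.2.1.2, pembrolizumab can resume only after the event has come down to Grade 1 or 0 and the steroid has been tapered. The taper lasts at least 4 weeks, which is 4 × 7 = 28 days against a 21-day cycle, so a taper alone spans at least one scheduled dose. Treatment stops permanently if the steroid cannot be brought down to 10 mg prednisone or equivalent per day within 12 weeks. A patient who never starts steroids is not subject to either rule. The trigger can therefore alter hold length and possibly discontinuation.

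**The case against.** The strongest reply is that Section 13.3.5, read literally, does yield a usable path. If the 3-day rule always fires first, the 1-week condition is dead text and everyone escalates after day 3. On days 4 to 7 without blood or mucus the 1-week bullet is not met, so a reader who infers that such a patient falls under both instructions would be wrong. Nor does that bullet forbid earlier steroids; the wait is inferred from its condition. These points stand. The defect is an unreachable trigger that invites different handling, and it is not an instruction impossible to carry out.

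It is also fair that the guidance presents itself as subject to clinical judgment and defers to the protocol, and that the Section 6.2.1.2 row lacks a waiting period only by silence. A reader might infer three flatly incompatible rules. The documents support less: a clear conflict inside Section 13.3.5, and a table that does not say whether any duration condition applies. Judgment and deference do not remove the internal conflict, because two written limits for the same symptom remain in the same list.

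**Conclusion.** The point holds as a wording conflict in a safety instruction. The 1-week condition can never apply first, and the consequence is possible inconsistency in steroid exposure, with a possible further effect on hold length and discontinuation. The conclusion rests on the plain reading of the Grade 3 heading and on no numerical assumption.

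A reader might infer more than the documents support:

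- **Event-of-clinical-interest reporting.** Steroid use and dose modification appear among the reporting criteria, but Grade 2 colitis or diarrhea already qualifies by grade in Sections 13.3.1 and 13.3.5, so the trigger cannot change its status.
- **Initial hold.** Both lists in Section 13.3.5 and the diarrhea/colitis row in Section 6.2.1.2 hold pembrolizumab at Grade 2.
- **Toxicity table.** Section 9.5 tabulates by type and severity, with CTCAE grades. The instruction to treat as Grade 3 concerns management and does not regrade the event.
- **A patient count.** The documents give neither the frequency nor the duration of Grade 2 diarrhea, so the number affected cannot be sized. Any assumed rate of Grade 2 diarrhea would give only an upper bound for the 3-day versus 1-week conflict, since short episodes never reach it.

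The response endpoint, the sample size and the error rates are untouched.

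**What to change.** Reconcile the two Grade 2 bullets and the Grade 3 heading in Section 13.3.5 with each other and with the diarrhea/colitis row in Section 6.2.1.2, so that one duration trigger and one action remain. The amended text should make clear whether the blood or mucus condition stands on its own, and whether the Section 6.2.1.2 row carries the same duration condition. The clinical team must decide which trigger and action to keep; this review takes no position on that. The cost is a protocol wording amendment, with no change to the design, data collection or analysis.

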13.3.6 Endocrine

The following AE terms, if considered \geq Grade 3 or if \geq Grade 2 and require holding/discontinuation/ modification of pembrolizumab dosing, are considered ECIs and should be reported to the Drug Manufacturer within 24 hours of the event:

- Adrenal insufficiency
- Hyperthyroidism
- Hypophysitis
- Hypopituitarism
- Hypothyroidism
- Thyroid disorder

- Thyroiditis

All attempts should be made to rule out other causes such as brain metastases, sepsis and/or infection. However the AE should be reported regardless of etiology.

Hypophysitis or other symptomatic endocrinopathy other than hypo- or hyperthyroidism

Grade 2 events:

- Report as ECI if appropriate
- Hold pembrolizumab
- Monitor thyroid function or other hormonal level tests and serum chemistries more frequently until returned to baseline values.
- Pituitary gland imaging should be considered (MRIs with gadolinium and selective cuts of the pituitary can show enlargement or heterogeneity and confirm the diagnosis).
- Treat with prednisone 40 mg p.o. or equivalent per day. When symptoms improve to Grade 1 or less, steroid taper should be started and continued over no less than 4 weeks. Replacement of appropriate hormones may be required as the steroid dose is tapered.
- Permanently discontinue for inability to reduce corticosteroid dose to 10 mg or less of prednisone or equivalent per day within 12 weeks.
- Consultation with an endocrinologist may be considered.

Grade 3 events:

- Report as ECI
- Hold pembrolizumab.
- Endocrine consultation is recommended.
- Rule out infection and sepsis with appropriate cultures and imaging.
- Treat with an initial dose of methylprednisolone 1 to 2 mg/kg intravenously followed by oral prednisone 1 to 2 mg/kg per day. When symptoms improve to Grade 1 or less, steroid taper should be started and continued over no less than 4 weeks. Replacement of appropriate hormones may be required as the steroid dose is tapered.
- Permanently discontinue for inability to reduce corticosteroid dose to 10 mg or less of prednisone or equivalent per day within 12 weeks.
- Hypophysitis with clinically significant adrenal insufficiency and hypotension, dehydration, and electrolyte abnormalities (such as hyponatremia and hyperkalemia) constitutes adrenal crisis.
- Hospitalization and endocrine consultation should be considered.

Grade 4 events:

- Report as ECI
- Discontinue pembrolizumab.
- Manage as per Grade 3

Hyperthyroidism and Hypothyroidism

Thyroid disorders can occur at any time during treatment. Monitor patients for changes in thyroid function (at the start of treatment, periodically during treatment, and as indicated based on clinical evaluation) and for clinical signs and symptoms of thyroid disorders.

Grade 2 events (and Grade 3-4 hypothyroidism):

- Report as ECI if appropriate (see Table 1)
- Monitor thyroid function or other hormonal level tests and serum chemistries more frequently until returned to baseline values.
- Thyroid hormone and/or steroid replacement therapy to manage adrenal insufficiency.
- Therapy with pembrolizumab can be continued while treatment for the thyroid disorder is instituted.
- In hyperthyroidism, non-selective beta-blockers (e.g. propranolol) are suggested as initial therapy.
- In hypothyroidism, thyroid hormone replacement therapy, with levothyroxine or liothyronine, is indicated per standard of care.
- Consultation with an endocrinologist may be considered.

Grade 3 hyperthyroidism events:

- Report as ECI
- Hold pembrolizumab.
- Rule out infection and sepsis with appropriate cultures and imaging.
- Treat with an initial dose of methylprednisolone 1 to 2 mg/kg intravenously followed by oral prednisone 1 to 2 mg/kg per day. When symptoms improve to Grade 1 or less, steroid taper should be started and continued over no less than 4 weeks. Replacement of appropriate hormones may be required as the steroid dose is tapered.
- Permanently discontinue for inability to reduce corticosteroid dose to 10 mg or less of prednisone or equivalent per day within 12 weeks.

Grade 4 events:

- Report as ECI
- Discontinue pembrolizumab.
- Manage as per Grade 3

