Subjects who experience a recurrence of the same severe or life-threatening event at the same grade or greater with re-challenge of pembrolizumab should be discontinued from trial treatment.

Table 3 Dose Modification and Toxicity Management Guidelines for Immune-related AEs Associated with Pembrolizumab

General instructions:				

 1. Corticosteroid taper should be initiated upon AE improving to Grade 1 or less and continue to taper over at least 4 weeks. 2. For situations where pembrolizumab has been withheld, pembrolizumab can be resumed after AE has been reduced to Grade 1 or 0 and corticosteroid has been tapered. Pembrolizumab should be permanently discontinued if AE does not resolve within 12 weeks of last dose or corticosteroids cannot be reduced to ≤ 10 mg prednisone or equivalent per day within 12 weeks. 3. For severe and life-threatening irAEs, IV corticosteroid should be initiated first followed by oral steroid. Other immunosuppressive treatment should be initiated if irAEs cannot be controlled by corticosteroids. 				
Immune-related AEs	Toxicity grade or conditions (CTCAEv4.0)	Action taken to pembrolizumab	irAE management with corticosteroid and/or other therapies	Monitor and follow-up
Pneumonitis	Grade 2	Withhold	
 • Administer corticosteroids (initial dose of 1-2 mg/kg prednisone or equivalent) followed by taper 	
 • Monitor participants for signs and symptoms of pneumonitis • Evaluate participants with suspected pneumonitis with radiographic imaging and initiate corticosteroid treatment • Add prophylactic antibiotics for opportunistic infections
	Grade 3 or 4, or recurrent Grade 2	Permanently discontinue		

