Hypothyroidism	Grade 2-4	Continue	
 Initiate thyroid replacement hormones (eg, levothyroxine or liothyronine) per standard of care 	
 Monitor for signs and symptoms of thyroid disorders.
Nephritis and Renal dysfunction	Grade 2	Withhold	
 Administer corticosteroids (prednisone 1-2 mg/kg or equivalent) followed by taper. 	
 Monitor changes of renal function
	Grade 3 or 4	Permanently discontinue		
Myocarditis	Grade 1 or 2	Withhold	
 Based on severity of AE administer corticosteroids 	
 Ensure adequate evaluation to confirm etiology and/or exclude other causes

	Grade 3 or 4	Permanently discontinue		
All other immune-related AEs	Intolerable/ persistent Grade 2	Withhold	
Based on type and severity of AE administer corticosteroids	
Ensure adequate evaluation to confirm etiology and/or exclude other causes
	Grade 3	Withhold or discontinue based on the type of event. Events that require discontinuation include and not limited to: Gullain-Barre Syndrome, encephalitis		
	Grade 4 or recurrent Grade 3	Permanently discontinue		

1. Withhold or permanently discontinue pembrolizumab is at the discretion of the investigator or treating physician.
 
NOTE:
 
For participants with Grade 3 or 4 immune-related endocrinopathy where withhold of pembrolizumab is required, pembrolizumab may be resumed when AE resolves to \leq Grade 2 and is controlled with hormonal replacement therapy or achieved metabolic control (in case of T1DM).
				

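### Grade 3–4 hyperthyroidism: the immune-related AE table and Section 13.3.6 disagree on treatment, on stopping pembrolizumab and on resumption, and neither clearly governs

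*Combined protocol and SAP*

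**What the plan says.** All references are to the combined protocol and SAP.

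**Section 6.2.1.2, immune-related AE table (the second table labelled Table 3)**

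- Hyperthyroidism row, treatment column: "Treat with non-selective beta-blockers (eg, propranolol) or thionamides as appropriate". No steroid is named in the row.
- Hyperthyroidism row, Grade 3 or 4, action on pembrolizumab: withhold or stop permanently. Footnote 1 adds: "Withhold or permanently discontinue pembrolizumab is at the discretion of the investigator or treating physician".
- General instruction 2 on resumption: "pembrolizumab can be resumed after AE has been reduced to Grade 1 or 0 and corticosteroid has been tapered". It also requires permanent discontinuation if the event has not resolved within 12 weeks of the last dose, or if steroid cannot be brought to 10 mg prednisone equivalent or less per day within 12 weeks.
- General instruction 3: "For severe and life-threatening irAEs, IV corticosteroid should be initiated first followed by oral steroid".
- NOTE under the table: "For participants with Grade 3 or 4 immune-related endocrinopathy where withhold of pembrolizumab is required, pembrolizumab may be resumed when AE resolves to" Grade 2 or lower and "is controlled with hormonal replacement therapy or achieved metabolic control (in case of T1DM").

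**Section 13.3.6, hyperthyroidism and hypothyroidism**

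- Grade 2: beta-blockers are suggested as first therapy for hyperthyroidism, and pembrolizumab can continue.
- Grade 3 hyperthyroidism: hold pembrolizumab. "Treat with an initial dose of methylprednisolone 1 to 2 mg/kg intravenously followed by oral prednisone 1 to 2 mg/kg per day". The taper starts at Grade 1 or less and lasts at least 4 weeks. The 10 mg, 12-week steroid limit applies.
- Grade 4: discontinue pembrolizumab, and otherwise manage as Grade 3.

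**Linking text**

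- Section 13.3.1 defines discontinuation as permanent and refers questions of dose modification and treatment to the protocol's own language.
- Section 6.2.1.2 refers the reader to Section 13.3 for managing adverse events.

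**The concern.** Two physicians who both follow this protocol could manage the same graded event differently. One, working from the hyperthyroidism row, would give a beta-blocker or thionamide and might withhold pembrolizumab with a view to restarting. The other, working from 13.3.6, would give high-dose systemic steroid at Grade 3 and stop pembrolizumab for good at Grade 4.

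At stake are steroid exposure, whether a patient may return to pembrolizumab, and on what conditions. Toxicity is a secondary objective (Section 4.2). Management that varies with the section consulted makes the toxicity and exposure data less uniform.

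**Working it through.** The plan states no figure on this point and no arithmetic applies. The check is a side-by-side reading of Sections 6.2.1.2, 13.3.1 and 13.3.6.

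| Question | Hyperthyroidism row, footnote and NOTE (6.2.1.2) | General instructions of the same table (6.2.1.2) | Section 13.3.6 |
|---|---|---|---|
| Treatment, Grade 3 | Beta-blocker or thionamide | IV then oral steroid if severe | IV methylprednisolone, then oral prednisone; beta-blocker listed only at Grade 2; thionamide not mentioned |
| Treatment, Grade 4 | Same cell | IV then oral steroid if life-threatening | As Grade 3 |
| Pembrolizumab, Grade 3 | Withhold or stop permanently, at discretion | – | Hold |
| Pembrolizumab, Grade 4 | Withhold or stop permanently, at discretion | – | Discontinue (permanent, per 13.3.1) |
| Resumption after a Grade 3 hold | Grade 2 or lower and controlled with hormone replacement | Grade 0–1 and steroid tapered; 12-week limits | Taper begins only at Grade 1 or less, over at least 4 weeks; 10 mg, 12-week limit |

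1. **Treatment.** Table 10 in Section 8.2.4 describes Grade 3 as severe and Grade 4 as life-threatening, so general instruction 3 reaches both grades. The table's row and its own general instruction therefore point in different directions. Section 13.3.6 sides with the general instruction.

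2. **Does the row's treatment cell cover Grade 3–4?** In the text as extracted, the cell sits on the Grade 2 line and the Grade 3–4 line has none. The pneumonitis, colitis, hypophysitis, nephritis and myocarditis rows extract the same way, while the AST/ALT row, where steroid dosing differs by grade, shows two cells. A shared cell is the sensible reading, but the extraction cannot prove it. Steps 3 and 4 do not depend on it.

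3. **Grade 4 action.** The table permits a hold with possible resumption, and the NOTE names Grade 4 explicitly. Section 13.3.6 closes that route. This is the sharpest of the conflicts.

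4. **Resumption after Grade 3.** The NOTE accepts Grade 2 or lower; general instruction 2 requires Grade 0–1 with steroid tapered. The NOTE also requires control by hormone replacement, which the table lists for hypothyroidism and hypophysitis but not for hyperthyroidism, so its application here is unclear. Section 13.3.1 adds a further difficulty: for resumption after a hold it cites Section 8.1.5.2.1, which governs a second course after complete response or 24 months of treatment, not return from a toxicity hold.

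5. **Precedence.** Section 13.3.1 defers to the protocol; Section 6.2.1.2 sends the reader to 13.3. Following either pointer leads back to the other section.

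**The case against.** The strongest reply is that a precedence rule already exists. Section 13.3.1 says the protocol's specific language governs dose modification and treatment, and describes its own recommendations as guidelines subject to clinical judgment. That narrows the conflict. It does not settle it, because 6.2.1.2 points back to 13.3 and because the table's row and general instruction 3 differ within the protocol body itself.

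A second reply is that the treatments need not exclude each other. The row's wording is permissive and does not forbid steroid, so it could be combined with general instruction 3 as symptomatic therapy plus steroid in severe cases. That is a possible reading, but the text does not state it. It would also leave the Grade 4 action and the resumption conditions unresolved.

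Some stronger readings are tempting, and the documents do not support them:

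- *That a patient managed under the table gets no steroid.* This is true of the row only; general instruction 3 calls for steroid in severe events.
- *That no 12-week limit applies without steroid.* General instruction 2 also has a limit on resolution of the event, which needs no steroid use.
- *That following 13.3.6 costs at least one extra dose*, because a taper of at least 4 weeks (28 days) exceeds the 21-day cycle. This assumes that the taper must be complete before restart. It also lacks a comparator: both sections allow or require a hold at Grade 3, and no hold length under the row is given.
- *That there are two competing routes back at Grade 4.* Section 13.3.6 has none; the conflict there is discretion against a permanent stop.

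**Conclusion.** The inconsistency is real and should be corrected. At Grade 3 the documents disagree on treatment and on the conditions for resuming pembrolizumab. At Grade 4 they disagree on treatment and on whether pembrolizumab can be resumed at all. The treatment disagreement rests partly on reading the row's cell as shared across grades, which is likely but unconfirmed; the disagreements over Grade 4 stopping and over resumption do not need that assumption.

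The size cannot be put as a number. The documents give no expected frequency of Grade 3–4 hyperthyroidism, and no defensible count of missed doses or steroid days follows from the text. For an affected patient the differences are substantial: systemic steroid or possibly none, and a hold that may end or a permanent stop. A reader might infer that the design or its operating characteristics are affected. They are not: nothing in Section 9.5 depends on this text. It is an internal inconsistency in clinical management, not a design choice.

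**What to change.** The sponsor's clinical team should reconcile the immune-related AE table in 6.2.1.2 (hyperthyroidism row, footnote 1, general instructions 2 and 3, NOTE), the dose-modification paragraph of 13.3.1, and the hyperthyroidism text in 13.3.6. For each grade of hyperthyroidism there should be one treatment instruction, one action on pembrolizumab and one resumption condition.

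The revision should also:

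- state whether the row's treatment cell applies to all listed grades;
- say whether the NOTE applies to hyperthyroidism and, if so, what counts as control;
- correct the cross-reference for resumption after a hold;
- state in both 6.2.1.2 and 13.3.1 which section governs when they differ.

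Which treatment, stopping rule and resumption rule are right is for the sponsor's clinicians; none is proposed here. The cost is wording in one table, one overview paragraph and one appendix list, with no change to sample size, endpoints or analysis.
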